12 PLANNED STATISTICAL METHODS

12.1 General Considerations

An incomplete block design will be adopted in this study with every subject being exposed to 2 out of the 3 study products (CC, THS 2.2, and NRT gum) to allow comparisons between THS 2.2 and CC in Group-1 (sequence 1 and 2), and between THS 2.2 and NRT gum in Group-2 (sequence 3 and 4).

Full details of the statistical analysis will be given in a SAP. Any changes to the planned statistical methods will be documented in the Clinical Study Report. The statistical evaluation will be performed using SAS[®], version 9.2 or later.

12.1.1 Stratification Criteria

For analysis, the following stratification criteria will be used:

- Sex (male and female)
- CC nicotine level at Admission (ISO nicotine levels ≤ 0.6 mg and 0.6 to 1 mg)

In addition, for the safety data, the analysis will be stratified by sequence and by study periods (Screening, product test, product exposure, and safety follow-up period).

12.1.2 Definitions for Statistical Data Analysis

Unless otherwise stated, for the purposes of statistical analyses, baseline is defined as the last available time point prior to T_0 on Day 1, from 6:00 AM to 9:00 AM.

12.1.3 Descriptive Statistics

All data will be presented in listings, ordered by sequence and subject, unless otherwise specified.

Descriptive statistics for continuous variables (number of subjects [n], number and percentage of subjects with missing data, mean, standard deviation, median, first and third quartiles, minimum and maximum for continuous data, and the n and absolute and relative [%] frequency for categorical data) will presented by exposure and overall at each time point, where applicable.

Descriptive statistics for PK parameters will also include the geometric mean and coefficient of variation (CV).

Philip Morris Products S.A.	Clinical Study Protocol	Confidential
ZRHR-PK-02-JP	Final 1.0 / 21 June 2013	Page 90 of 122

Baseline, admission and screening data (i.e., anything prior to product exposure) will be summarized by sequence and overall where appropriate

12.1.4 Handling of Missing Values and of Values outside the Detection Limits

In general, missing data will not be imputed in this study, due to the nature of the measurements and the short periods of exposure and use. However, for questionnaire data total scores and domain or subscale scores may use a certain degree of imputation by averaging across individual item scores. Further details will be provided in the SAP.

Values below the lower limit of quantification (LLOQ) will be imputed using 0.5 x LLOQ. For values above the upper limit of quantification (ULOQ), i.e., preceded by a ">", for example ">xx", the numerical xx will be used for calculation and reporting in summary tables. The number of values below LLOQ or above ULOQ will be presented in each summary table.

12.1.5 Significance Level for Inferential Analysis

For all endpoints, unless otherwise stated, statistical tests will be two-sided and conducted at the 5% significance level and all quoted confidence intervals will be two-sided 95% CIs.

No formal adjustment of the test-wise alpha level for multiple testing is necessary, as no claim will be made based on the outcome of the individual tests.

12.2 Determination of Sample Size and Power Consideration

A total of 62 subjects will be randomized. This sample size is the sum of the sample size requirements for the THS 2.2:CC comparison and the THS 2.2:NRT gum comparison (as described in detail below).

The estimates for the within-subject CV for nicotine C_{max} (36%) and AUC_(0-last) (21%) are based on the data collected in the ZRHX-PK-02 clinical study (ZRHX-PK-02, 2012) comparing the nicotine PK profiles of Tobacco Heating System 2.1, the predecessor of THS 2.2 (regular tobacco stick) and CC. In the absence of data comparing THS and NRT gum, the same CVs were assumed for the calculation of the sample size related to the THS 2.2:NRT gum comparison.

Anticipated mean C_{max} and $AUC_{(0-last)}$ for THS 2.2 and CC were based on data from the ZRHX-PK-02 study (ZRHX-PK-02, 2012). Anticipated mean C_{max} and $AUC_{(0-last)}$ for NRT gum were based on data reported by Dautzenberg et al., 2007.

The sample sizes of this study assume a drop-out rate no larger than 10%.

Philip Morris Products S.A.	Clinical Study Protocol	Confidential
ZRHR-PK-02-JP	Final 1.0 / 21 June 2013	Page 91 of 122

Sample size calculations were conducted using SAS[®] version 9.2 for the 95% CI of the mean differences between paired observations (proc power onesamplemeans) in the natural log scale (Senn, 2002). The SAS[®] implementation of the method published by Beal, 1989 was adopted to estimate the probability of obtaining at most the target 95% CI of $\pm 20\%$.

THS 2.2:CC comparison

A total of 44 subjects are needed to estimate the mean C_{max} parameter ratio between THS 2.2 and CC with a 90% probability of obtaining a margin of error (95% CI) of at most ±20%, assuming that THS 2.2 have a nicotine C_{max} similar to CC (ratio equal to 1.00). This sample size is sufficient to provide 90% probability of obtaining a margin of error of at most ±20% for the AUC_(0-last) ratio between THS 2.2 and CC, assuming a similar extent of nicotine absorption for the 2 products (ratio equal to 1.00).

THS 2.2:NRT gum comparison

A total of 18 subjects are needed to estimate the mean AUC_(0-last) parameter ratio between THS 2.2 and NRT gum with a precision allowing for the lower bound of the 95% CI exceeding 1.00, with 90% power, assuming a geometrical ratio between THS 2.2 and NRT gum of 1.28. This sample size is sufficient to provide 90% power of obtaining a lower bound of the 95% CI of C_{max} ratio between THS 2.2 and NRT gum, exceeding 1.00, assuming a geometrical mean ratio between THS 2.2 and NRT gum of 2.00.

12.3 Analysis Populations

All analyses will be based on actual product exposure. All endpoints (other than safety) will be analyzed using the PK analysis sets. Safety will be analyzed using the safety population.

12.3.1 PK Populations

The analysis populations for the PK endpoints are composed of two analysis sets to allow the comparison between THS 2.2 and NRT gum separately from the comparison between THS 2.2 and CC.

The PK populations consist of all the randomized subjects who give informed consent, completed at least one of the single use Day 1 or Day 3, and for whom at least one PK parameter can been derived. Only subjects without major protocol deviations (to be defined in the SAP) will be included in the PK analysis sets.

12.3.2 Safety Population

The safety population consists of all the subjects who give informed consent and have at least one exposure to THS 2.2 (including the product test at Admission Day).

Philip Morris Products S.A.	Clinical Study Protocol	Confidential
ZRHR-PK-02-JP	Final 1.0 / 21 June 2013	Page 92 of 122

12.4 Demographics and Baseline Characteristics

Demographic and other baseline characteristics will be reported for the PK and safety populations. Appropriate summary statistics will be provided as described in Section 12.1.3.

12.5 Primary Endpoints

12.5.1 Primary Endpoint Analysis Variables

Nicotine PK parameters will be derived from plasma nicotine versus time data using a non-compartmental technique. In particular:

C _{max}	Maximum observed plasma concentration. C_{max} will be reported as long as there is at least one quantifiable concentration post-exposure
AUC _(0-last)	Area under the plasma concentration-time curve from start of product use to the time of the last quantifiable concentration (linear trapezoidal

12.5.2 Baseline Comparability

method).

Not applicable.

12.5.3 Descriptive Analysis

Primary endpoints will be summarized as described in Section 12.1.3.

An analysis of variance (ANOVA) will be conducted on $AUC_{(0-last)}$ and C_{max} endpoints in the natural logarithmic scale. The model will include terms for sequence, subjects within sequence, period and product exposure as fixed effect factors. The results of this analysis for each of $AUC_{(0-last)}$ and C_{max} are presented in terms of adjusted geometric least square means and 95% CIs for the THS 2.2 :CC and THS 2.2:NRT gum ratios.

This approach is consistent with the guidelines in the European Medicines Agency's guidelines for bioequivalence investigations (EMA, 2008) and FDA's Center for Drug Evaluation and Research (FDA, 2001). Carry-over effect will not be tested, as it cannot be statistically distinguished from the interaction between treatment and period in a 2x2 crossover design (ICH E9, 1998).

A sensitivity analysis will be conducted should there be 20% or more missing PK parameter values, by repeating the above analyses using mixed effects ANOVA model in the natural log scale, with a restricted maximum likelihood method to estimate mean differences and

Confidentiality statement: Data and information contained in this document are considered to constitute trade secrets and confidential commercial information, and the legal protections provided to such trade secrets and confidential information are hereby claimed under the provisions of applicable law. No part of this document may be publicly disclosed without the written consent of Philip Morris Products S.A.

Philip Morris Products S.A.	Clinical Study Protocol	Confidential
ZRHR-PK-02-JP	Final 1.0 / 21 June 2013	Page 93 of 122

variances as suggested by FDA (FDA, 2001). Subjects within sequence will be used as random effects and fixed effects are period, sequence, and product exposure. To evaluate the sensitivity to the distributional assumptions, point and interval estimates will also be estimated by means of the percentile bootstrap technique, using 2000 bootstrap samples which preserve the number of subjects per sequence.

12.5.4 Confirmatory Analyses

Given that the objective of this study is to determine the point estimate and precision of the ratio of THS 2.2:CC for C_{max} and $AUC_{(0-last)}$, there is no statistical hypothesis to be tested.

12.6 Secondary Endpoints

12.6.1 Secondary Endpoint Analysis Variables

Nicotine PK parameters will be derived as follows:

- t_{max} Time of maximum observed plasma concentration. t_{max} will be reported as long as there is at least one quantifiable concentration post-exposure
- AUC_(0-t') Area under the plasma concentration-time curve from start of product use to the subject-specific time of maximum nicotine concentration following CC or NRT gum (linear trapezoidal method)
- $AUC_{(0-\infty)}$ Area under the plasma concentration-time curve from start of product use extrapolated to infinite time, according to:

$$AUC_{0-\infty} = AUC_{0-last} + \left(\frac{C_{last}}{\lambda z}\right)$$

Where C_{last} is the last quantifiable concentration and λ_z is the terminal elimination rate constant

- λ_z Terminal elimination rate constant, estimated by linear regression analysis of the natural log-transformed concentration-time data
- $t_{1/2}$ Terminal elimination half-life, derived as $ln(2)/\lambda_z$

More details on PK parameter derivations will be provided in the SAP.

Confidentiality statement: Data and information contained in this document are considered to constitute trade secrets and confidential commercial information, and the legal protections provided to such trade secrets and confidential information are hereby claimed under the provisions of applicable law. No part of this document may be publicly disclosed without the written consent of Philip Morris Products S.A.

Philip Morris Products S.A.	Clinical Study Protocol	Confidential
ZRHR-PK-02-JP	Final 1.0 / 21 June 2013	Page 94 of 122

Subjective effects of using THS 2.2 as compared to CC and NRT gum will be evaluated by analyzing domain scores of the QSU-brief and MCEQ. Full details of questionnaire domain scores derivation will be provided in the SAP.

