7.1.2 Calculation of AUC

The minimum requirement for the calculation of the AUC is the inclusion of at least 3 consecutive plasma concentrations above the lower limit of quantification (LLOQ), with at least 1 of these concentrations following C_{max} .

AUC_(0-last) and AUC_(0-t') will be calculated using the linear trapezoidal method.

AUC_(0-t') will be calculated automatically by linear interpolation within WinNonlin, where t' is the subject-specific actual time of maximum nicotine concentration following single

Statistical Analysis Plan Final v 2.0 / 07 April 2014 Confidential

Page 20 of 73

use of the CC or NRT gum product, between the THS 2.2 and CC, as well as the THS 2.2 and NRT gum.

 $AUC_{(0-\infty)}$ will be calculated as follows:

$$AUC_{0-\infty} = AUC_{0-last} + \left(\frac{C_{last}}{\lambda_z}\right)$$

Where C_{last} is the last quantifiable concentration and λ_z is the terminal elimination rate constant.

%AUC_{extrap}, the percentage of AUC_(0- ∞) extrapolated beyond t_{last} , will be calculated according to the following formula:

$$\%AUC_{extrap} = \left(1 - \frac{AUC_{0-last}}{AUC_{0-\infty}}\right) \times 100$$

 $AUC_{(0-\infty)}$ values where the percentage extrapolation is greater than 20% will be flagged in the data listings and will be reviewed for inclusion in the analysis during the ore-analysis data review.

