11.6.2.1.1 THS 2.2 vs CC

Only subjects in the Group-1 PK population will be included in the following analyses.

The secondary analysis of AUC_(0-∞), AUC_(0-t') and t_½ will be performed on the natural log-transformed parameters using the same ANOVA model as used for the primary analysis. (Section 11.6.1 "Primary Analyses"). Only subjects in the Group 1-PK population who provide evaluable data for both the THS 2.2 and CC products will be included in the analyses.

Statistical Analysis Plan Final v 2.0 / 07 April 2014 Confidential

Page 46 of 73

Supportive analysis will be performed as described in Section 11.6.3 "Supportive/Sensitivity Analysis" in order to evaluate the sensitivity of THS 2.2 effect estimates to methods used for missing data by means of a mixed model approach, should there be 20% or more missing parameter PK model.

The analysis of t_{max} will be performed by calculating the difference for each subject (THS 2.2 - CC) and obtaining the Hodges-Lehmann (Hodges and **Lehmann**, 1963) 95% CI estimates. The median t_{max} for each product and the median difference between the products along with the 95% CI will be presented in the tables. Supportive analysis will be performed as described in Section 11.6.3 "Supportive/Sensitivity Analysis" in order to evaluate the THS 2.2 effect estimates on t_{max} adjusted for period, sequence, and subject within sequence.

The data will be presented in the below outputs:

TFL	Title
number	
TABLES	
15.2.4.1	Analysis of Secondary Pharmacokinetic Parameters of Nicotine -
	Group-1 PK Population

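### AUC(0-t') stops both curves at the reference product's own tmax, so identical products are expected to give a THS 2.2:reference ratio below 1

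*Protocol*

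**What the plan says.** Protocol 12.6.1 defines AUC(0-t') as the area from start of product use "to the subject-specific time of maximum nicotine concentration following CC or NRT gum". SAP 7.1.2 keeps this definition: the parameter "will be calculated automatically by linear interpolation within WinNonlin, where t' is the subject-specific actual time of maximum nicotine concentration following single" (the sentence then names CC or gum). The area "will be calculated using the linear trapezoidal method". One reference-derived time per subject therefore cuts both of that subject's curves.

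The parameter serves the secondary objective of evaluating the difference in absorption between THS 2.2 and each comparator (Protocol 3.2). SAP 11.6.2.1.1 analyses the "log-transformed parameters using the same ANOVA model" as the primary endpoints, and 11.6.2.1.2 does the same against gum. Protocol 12.5.3 gives the model: "The model will include terms for sequence, subjects within sequence, period and product exposure as fixed effect factors". Protocol 12.1.5 adds that "all quoted confidence intervals will be two-sided 95% CIs". Neither document says what ratio to expect when the products do not differ.

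**The concern.** A reader of a THS 2.2:CC ratio with a 95% CI takes 1 to mean no difference. Here 1 is not that value. When the reference happens to peak early, the THS 2.2 curve is cut while still rising and loses a lot of area. When the reference peaks late, THS 2.2 is already past its peak and gains less. On the log scale the loss exceeds the gain, so the average lies below 0 even for exchangeable products.

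At stake is how one secondary result is read. Some or all of an apparent shortfall in early nicotine exposure with THS 2.2 could come from how t' is chosen.

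**Working it through.** **The plan's own figure.** Nothing is stated for AUC(0-t'). The nearest figure is the Group-1 size of 44, which rests on a within-subject Cmax CV of 36% (Protocol 12.2). The SD of a paired log difference is √(2·ln(1 + 0.36²)) = 0.494. With 40 pairs, the probability that the 95% CI half-width is at most ln 1.2 is about 92%. Since 44 × 0.9 = 39.6, the figure of 44 reproduces, and 40 evaluable pairs is a fair working number.

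**Why the ratio falls below 1.** Take the simplest curve, a linear rise to a plateau, the same for both products, with times to peak differing by a factor e^d.
- Reference peaks earlier by d: THS 2.2 area ÷ reference area = e^(−d), so the log ratio is −d.
- Reference peaks later by d: the ratio is 2 − e^(−d), so the log ratio is ln(2 − e^(−d)).

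At d = 0.3 these are −0.300 and ln(1.259) = +0.230. Their mean is −0.035, a ratio of 0.966. Let the log time to peak have within-subject SD σ, so that the difference is normal with SD √2·σ. Averaging over it gives 0.992 / 0.972 / 0.946 / 0.915 / 0.882 for σ = 0.1 / 0.2 / 0.3 / 0.4 / 0.5.

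**Simulation on the protocol's sampling times.** From the documents:
- THS 2.2/CC sampling grid (Protocol 7.5.1.2)
- linear trapezoid (SAP 7.1.2)
- terminal half-life of 2 h (Protocol 4.2)
- Cmax CV near 36% (Protocol 12.2)

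Assumed:
- identical products, 20 pairs per sequence, crossover contrast on 40 − 2 = 38 df
- zero-order input averaging 6 min, with between-subject log-SD of duration 0.2
- distribution half-life 8 or 20 min, assay noise 8%
- within-subject amplitude log-SD 0.33, giving a simulated Cmax CV of about 34–36%
- within-subject log-SD of absorption duration as tabulated

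| Assumed log-SD | Ratio, identical products | 95% CI excludes 1 (nominal 5%) |
|---|---|---|
| 0.1 | 0.99 | about 5% |
| 0.2 | 0.975 | 5–6% |
| 0.3 | 0.95 | 8–9% |
| 0.4 | 0.925 | 11–13% |
| 0.5 | 0.90 | 15–17% |

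The rates move by a percentage point or two with curve shape and simulation error. From about 0.3 upward, nearly all exclusions are on the low side.

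**Is the choice of t' the cause?** In one scenario with log-SD 0.3, t' from CC gave 0.945. Taking t' from THS 2.2 instead gave 1.056, close to the mirror image (1 ÷ 0.945 = 1.058). One cut-off common to both products gave 0.994–1.002 across settings, with about 5% exclusion. With no within-subject timing variation and no assay noise, the subject-specific version gave 1.000. Assay noise alone moved it to about 0.96–0.999, because the observed maximum is then partly chosen by error.

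**Does anything planned remove it?** Sequence and period terms cannot, because t' comes from the reference in every sequence. The supportive analyses in SAP 11.6.3 (exclusion on T0 above 5% of Cmax, mixed model, bootstrap, zero-second imputation) all leave t' as defined.

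**Group-2.** With 18 subjects and identical profiles, a log-SD of 0.3 gave ratios of 0.93–0.97 and 0.5 gave 0.88–0.92. This shows direction more than size, because identical products are not a realistic case against gum: planning assumes a Cmax ratio of 2.00.

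**The case against.** The strongest reply is that nothing turns on whether this interval contains 1. SAP 5.4.1 lists the hypotheses: Cmax, AUC(0-last) and tmax, all against gum. AUC(0-t') is not among them, and no hypothesis is set against CC. Protocol 12.6.3 is headed as descriptive and 12.6.4 is not applicable. Protocol 12.1.5 and SAP 11.1.7 say no claim will rest on individual tests. This stands. A reader might infer that the trial plans a test that would falsely declare lower early exposure with THS 2.2; the documents plan no such test and no such statement. Bias still damages an estimate and its interval, whether or not a test is attached.

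Second, exposure up to the subject's own reference peak is a legitimate quantity, clearly defined and consistently applied. That also stands, so the parameter need not be dropped or demoted. What is missing is a caution that its ratio is not 1 for identical products, given that the objective is a product difference.

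Third, the size is unknown. At a log-SD of 0.2 to 0.3 the CI spans a factor of roughly 1.17–1.20 each way, so a shift of 2–5% sits well inside it. This is right, and it limits the point. Larger exclusion rates can be produced, but mostly by assuming a Cmax CV of about 21–27%, below the planned 36%, which makes the intervals too narrow.

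Fourth, SAP 11.6.2.1 already plans concentrations by time point and mean profiles, and 11.6.2.1.1 and 11.6.2.1.2 give the tmax difference. These help a careful reader, but they give no early-exposure ratio with a CI centred on no difference.

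**Conclusion.** The point holds as a directional bias in one secondary estimate. For identical products the expected AUC(0-t') ratio is below 1 whenever time to peak varies within subjects. In Group-1 the shift runs from about 1% at a log-SD of 0.1 to about 10% at 0.5: negligible at 0.1 to 0.2, material from about 0.3. The direction follows from the definition of t'. The size rests on a within-subject tmax variability that the documents do not give, and on the assumed curve shape and assay error.

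Against gum the lean runs the same way, which works against showing higher early exposure with THS 2.2. A reader might infer that the trial's main conclusions are affected. They are not: the success criterion and sample size concern Cmax and AUC(0-last), and none of the listed hypotheses uses t'.

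**What to change.** In SAP 7.1.2, 11.6.2.1.1 and 11.6.2.1.2, add a partial AUC for both products to one common time per group: the median CC tmax in the Group-1 PK population and the median gum tmax in the Group-2 PK population. Analyse it with the same ANOVA, report it beside the protocol-defined AUC(0-t'), and use it to interpret any difference in early exposure. State in the SAP and in the table footnotes that the subject-specific AUC(0-t') ratio is expected to fall below 1 for identical products. Record the addition in SAP section 9.

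The cost is one derived parameter from concentrations already collected and one row in each of Tables 15.2.4.1 and 15.2.4.2. A common cut-off is less tailored to each subject's reference peak. In Group-2 the different THS 2.2 and gum sampling times may leave a small residual difference, a ratio of about 0.98–1.00 for identical profiles, which the footnote should mention.

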12.6.2 Baseline Comparability

Not applicable.

12.6.3 Descriptive Analysis

In general, secondary endpoints will be summarized using the approach described in Section 12.1.3.

The following analyses will be conducted in both Group-1 and Group-2 PK analysis sets:

- The AUC_(0- ∞), AUC_(0-t'), and t_{1/2} will be analyzed using the same approach adopted for the primary endpoints. No statistical analysis will be performed on the elimination rate constant λ_z . Data will be summarized and presented together with 95% CI.
- The Hodges-Lehmann 95% CI estimates for the median t_{max} differences will be presented (Lingling, 2008).
- The use of random effects model is suggested in the context of the analysis of subjective effects of smoking (Shiffman et al., 2004). Mixed effects ANOVA with the same model terms as planned for the sensitivity analysis of the primary endpoints will be adopted for the analysis of QSU-brief, including all of the different assessment time points as repeated measurements. The analysis will not be adjusted for the assessment prior to T₀ (Fleiss et al, 1985).
- Levels of exhaled CO and of blood COHb will be summarized by means of descriptive statistics reported by exposure. Analysis of COHb levels will be conducted using a mixed model for repeated measures, the same approach as for the QSU-brief.

The following analyses will be conducted only in Group-1 PK analysis set:

• Mixed effects ANOVA with the same model terms as planned for the sensitivity analysis of the primary endpoints will be adopted for the analysis of the MCEQ domain scores.

The following analyses will be conducted in only Group-2 PK analysis set:

• To test if the time to the maximum nicotine concentration in THS 2.2 is shorter than in NRT gum the following hypothesis will be evaluated:

Philip Morris Products S.A.	Clinical Study Protocol	Confidential
ZRHR-PK-02-JP	Final 1.0 / 21 June 2013	Page 95 of 122

 $H_0: X_{THS} - X_{NRT} = 0$ $H_A: X_{THS} - X_{NRT} < 0$

where X_{THS} and X_{NRT} are the median values of the THS 2.2 and NRT gum, respectively. The t_{max} will be analyzed on the original scale using the Wilcoxon Signed-Rank Test with a type I error $\alpha = 0.025$ (one-sided test), as values are ordinal/discrete, and the assumption of normality may be questionable.

• To determine if the rate and the amount of nicotine absorbed of the THS 2.2 is higher relative to NRT gum the following hypothesis will be tested for both C_{max} and AUC_(0-last) parameters:

 $H_0: X_{THS} / X_{NRT} = 1.0$ $H_A: X_{THS} / X_{NRT} > 1.0$ where X_{THS} and X_{NRT} are the adjusted geometrical means of THS 2.2 and NRT gum, respectively. H_0 is rejected with a type I error $\alpha = 0.025$ (one-sided test), if the lower bound of the 95% CI for the X_{THS} / X_{NRT} ratio is higher than 1.0.

